### 9.2.2 Exclusion criteria

Patients meeting any of the following criteria will not be included in the study:

- Cancers other than breast cancer
- Male breast cancer
- Indications other than mentioned in the protocol
- Visceral crisis

Overall, physicians will capture data from approximately 150 patients on demographics, clinical characteristics, disease history, treatment history, palbociclib dosing, clinical outcomes and post-palbociclib combination therapy treatment data. The study will be descriptive in nature therefore no control or comparator groups will be included.

### 9.3 Variables

**Table 1. List of Study Variables**

Variable	Role	Data Source(s)	Operational Definition
Patient demographics	Baseline Sub-group identifier	Patient records	Age, ethnicity, weight, height, biomarker status, family history of breast cancer.
Clinical characteristics	Baseline Sub-group identifier	Patient records	Time since diagnosis, staging, node status, menopause status. ECOG/Karnofsky functional status, diagnosis for which palbociclib combination was prescribed, sites of metastases, de novo vs. recurrent disease.
Comorbid conditions	Baseline Sub-group identifier	Patient records	Comorbid conditions.
Early treatment history	Baseline Sub-group identifier	Patient records	Adjuvant treatments received since breast cancer diagnosis, time since end of adjuvant treatment, surgery/radiotherapy received.
Advanced treatment history	Baseline Sub-group identifier	Patient records	Treatments and supportive therapies received since metastatic/advanced HR+/HER2- diagnosis, duration of treatments, reasons for regimen changes.
Palbociclib combination treatment	Exposure Sub-group identifier	Patient records	Starting dose, duration of treatment, line of treatment, changes in dose, interruptions, cycle delays and discontinuations; where possible reasons for change in treatment.
Clinical outcomes	Outcomes	Patient records	Proportion progression free, ORR, TTP, PFS, patient death, 1-year and 2-year survival in all patients and within specific subgroups.

PFIZER CONFIDENTIAL

#### 9.4 Data Sources

Medical records collected through routine clinical care will be used as the data source for the study.

#### 9.5 Study Size

The study will recruit approximately 10 physicians from the routine clinical practices in India who will capture data from a total of approximately 150 patients.

**Table 2. Sample Size for Medical Record Review**

City	Approximate Number of Physicians	Number of Patient Records
Mumbai	1	20
Pune	1	10
Delhi	2	40
Bangalore	2	20
Kolkata	1	10
Vellore	1	10
Jaipur	1	20
Chennai	1	20
Total (approximate):	10	150

The sample size above (city, physician number per city, number of patient records and total samples) should be considered flexible, with scope to increase based on availability of medical records with each participating physician/site.

The objectives do not state any hypotheses and therefore, do not require any statistical testing. All the analyses will be descriptive and so sample size calculations are not required.

## **9.6 Data Management**

Physician reported data from the eCRF will be transferred to a single electronic data capture (EDC) tool. All data will be de-identified and anonymized. Incomplete data may be excluded from analysis following discussion with Pfizer. Any data related queries/ambiguities will be resolved in consultation with physician.

The database will be housed in a physically and logically secure computer system maintained in accordance with a written security policy. Patient confidentiality will be strictly maintained.

### **9.6.1. Case report forms (CRFs)/Data collection tools (DCTs)/Electronic data record**

As used in this protocol, the term CRF should be understood to refer to either a paper form or an electronic data record or both, depending on the data collection method used in this study.

A CRF is required and should be completed for each included patient. The completed original CRFs are the sole property of Pfizer and should not be made available in any form to third parties, except for authorized representatives of Pfizer or appropriate regulatory authorities, without written permission from Pfizer. The investigator shall ensure that the CRFs are securely stored at the study site in encrypted electronic form and will be password protected to prevent access by unauthorized third parties.

The investigator has ultimate responsibility for the collection and reporting of all clinical, safety, and laboratory data entered on the CRFs and any other data collection forms (source documents) and ensuring that they are accurate, authentic/original, attributable, complete, consistent, legible, timely (contemporaneous), enduring, and available when required. The CRFs must be signed by the investigator or by an authorized staff member to attest that the data contained on the CRFs are true. Any corrections to entries made in the CRFs or source documents must be dated, initialed, and explained (if necessary) and should not obscure the original entry.

The source documents are the hospital or the physician's chart. In these cases, data collected on the CRFs must match those charts.

### **9.6.2. Record retention**

To enable evaluations and/or inspections/audits from regulatory authorities or Pfizer, the investigator agrees to keep records, including the identity of all participating patients (sufficient information to link records, e.g., CRFs and hospital records), all original signed informed consent/assent documents, copies of all CRFs, safety reporting forms, source documents, detailed records of treatment disposition, and adequate documentation of relevant correspondence (e.g., letters, meeting minutes, and telephone call reports). The records

PFIZER CONFIDENTIAL

should be retained by the investigator according to local regulations or as specified in the clinical study agreement (CSA), whichever is longer. The investigator must ensure that the records continue to be stored securely for so long as they are retained.

If the investigator becomes unable for any reason to continue to retain study records for the required period (e.g., retirement, relocation), Pfizer should be prospectively notified. The study records must be transferred to a designee acceptable to Pfizer, such as another investigator, another institution, or to an independent third party arranged by Pfizer.

Study records must be kept for a minimum of 15 years after completion or discontinuation of the study, unless IQVIA and Pfizer have expressly agreed to a different period of retention via a separate written agreement. Record must be retained for longer than 15 years if required by applicable local regulations.

The investigator must obtain Pfizer's written permission before disposing of any records, even if retention requirements have been met.

## **9.7 Data Analysis**

Detailed methodology for summary and statistical analyses of data collected in this study will be documented in a statistical analysis plan (SAP), which will be dated, filed and maintained by the sponsor. The SAP may modify the plans outlined in the protocol; any major modifications of primary endpoint definitions or their analyses would be reflected in a protocol amendment.

All analyses are to be descriptive and so all methods to be used will reflect this descriptive nature. The specific method that will be used depends on type of variable being analyzed and those methods are:

- Categorical variables – will be described using:
  - Number of observations (n);
  - Number and percent (%) within each category;
  - Number of missing observations.
- Numeric variables – will be described using:
  - Number of observations (n);
  - Mean & Standard deviation;
  - Minimum, Maximum, Median and 1st & 3rd Quartiles;
  - Number of missing observations.

PFIZER CONFIDENTIAL

- Time to event – will be described using:
  - A Kaplan-Meier chart that will visually estimate the distribution of times to some events, eg, progression, and will consider those patients for which the event has not yet occurred;
  - 1-year and 2-year rates, median or some more appropriate percentiles if the median time is not reached in the sample.

Missing data will be excluded on a case by case basis and will not be imputed. This will mean that each table will not necessarily be based on the same number of patients.

All statistical analyses will be conducted with general purpose statistical software (SAS) version 9.0 or higher

PFIZER CONFIDENTIAL

Palbociclib

A5481145, PD-0332991 NON-INTERVENTIONAL STUDY PROTOCOL

Final Protocol version 1.0, 19-Oct-2020

CCI

PFIZER CONFIDENTIAL

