### Primary objectives

- To describe the demographics and clinical characteristics of patients who have received palbociclib combination with aromatase inhibitor (as prescribed by the Physician) in menopausal state as initial endocrine therapy in MBC or with fulvestrant after progression on prior endocrine therapy.
- To summarize adjuvant therapies received for the treatment of early or locally advanced breast cancer (Stages 0-IIIa).
- To describe treatments received in the advanced/metastatic setting, before and after palbociclib combination use.
- To describe dosing and dose changes, interruptions, delays, and discontinuations associated with palbociclib use in clinical practice.
- To describe supportive therapies received by patients while receiving palbociclib combination treatments.
- To determine in overall population and defined subgroups, clinical outcomes including (but not limited to):
  - Proportion of patients who are progression free at specific intervals (eg, 6, 12, 18 months).
  - Objective response rate (ORR) - depending on availability of follow-up data.
  - Proportion of alive patients 1 and 2 years post palbociclib combination initiation - depending on availability of follow-up data (sample size permitting).

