## 9.8 Quality Control

To improve data quality the following actions will be undertaken:

- Provision of standardized instructions on study design, methodology and procedures.
  - Physicians will be contacted via email or telephone and an overview of the study will be provided (detailing study objectives, patient inclusion criteria, correct completion of eCRF and interview and any other logistical aspects of the study).
  - Follow-up with the physicians to ensure queries are resolved quickly.
- The electronic materials will be tested thoroughly to ensure that all questions appear correctly on screen, allow easy interpretation/completion and that all routing and logic checks are working correctly. As such, there should be no missing data (given the online nature of the study, the physician will have to complete a question before he/she is able to move on the next) however, ‘don’t know or unknown’ will be valid responses.
- To improve and secure data quality, automatic data checks upon data entry will be done within the eCRF. In the eCRF, plausible ranges of values for numeric data entries as well as logical data entries and listings will be provided for each entry field. Based on this, checks on completeness and plausibility will be performed upon data entry in the eCRF. All corrections will be visible from the systems audit trail.
- No regular monitoring or source data verification is planned in this study. However, in case of decreasing compliance (ie, of missing data, data discrepancies, protocol violations, etc.) a for-cause audit or risk-based monitoring visit will be performed.

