6 HANDLING OF MISSING VALUES

No imputation for missing values will be performed.

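### The no-imputation rule has no exception for progression and death dates, so a known but undated event drops out of the Kaplan-Meier analysis while event-free women stay in

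*Protocol*

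**What the plan says.** Protocol 9.7 lists the methods for categorical, numeric and time-to-event variables and then gives one rule for all of them: "Missing data will be excluded on a case by case basis and will not be imputed". It accepts the consequence: "This will mean that each table will not necessarily be based on the same number of patients". SAP section 6 consists of a single sentence: "No imputation for missing values will be performed".

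For time to event, Protocol 9.7 plans a Kaplan-Meier chart that "will consider those patients for which the event has not yet occurred", with "1-year and 2-year rates, median or some more appropriate percentiles if the median time is not reached in the sample". A count of missing observations is required for categorical and numeric variables but is not listed for time to event.

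The primary objectives include "Proportion of patients who are progression free at specific intervals (eg, 6, 12, 18 months" months) and the proportions alive at 1 and 2 years, the latter subject to available follow-up and sample size. Protocol Table 1 lists the outcomes as "Proportion progression free, ORR, TTP, PFS, patient death, 1-year and 2-year survival".

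Protocol 9.8 argues from forced entry in the eCRF: "As such, there should be no missing data". The same sentence accepts don't know or unknown as an answer. SAP mock Table 1 records death as yes or no, and the protocol abstract lists date of death as a separate item. An event can therefore be on file without its date.

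**The concern.** An event-free woman needs only a last-contact date to contribute to the curve, and eligibility already requires 3 or 6 months of follow-up data. A woman who progressed or died needs an event date. If it is unknown and may not be imputed, the rule as written leaves no way to place her on the curve and she is excluded. The exclusion then depends on having had the event, which is the outcome being estimated.

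The progression-free proportions and the 1- and 2-year survival proportions are at stake. The loss would also be hard to see: no count of missing event dates is required, and the visible text has no sensitivity analysis that would reveal it.

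**Working it through.** **No figure to reproduce.** The plan gives no event count, precision target or expected Kaplan-Meier value. The check concerns direction first, then size.

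**Direction.** Let m be the share of women with an observed event whose date is unusable, c the share of event-free women without a last-contact date, and q(t) the share of women at risk at t whose event is later observed. If missingness does not depend on the event time, exclusion changes the estimated hazard by the factor

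(1 − m) / [1 − m·q(t) − c·(1 − q(t))].

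This is below 1 exactly when m > c. It equals 1 when m = c, so equal missingness gives no bias.

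**Inputs from the protocol.** Median progression-free survival of 24.8 months (letrozole combination) and 9.5 months (fulvestrant combination), section 7; first to later line about 7:3, section 9.1; about 150 women, section 9.5; minimum follow-up of 6 and 3 months, section 9.2.1.

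**Assumptions.** Exponential times; uniform follow-up of 6–47 months (aromatase inhibitor) and 3–34 months (fulvestrant); m from 5% to 30%; c = 0.

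**Hand check at m = 20%.** About 55.3% of women have an observed event, so the factor at time zero is 0.8 / (1 − 0.2 × 0.553) = 0.8 / 0.889 = 0.90. With complete dates, 6-month progression-free survival is 78.6%; 0.786^0.90 = 0.805. The simulation gives 80.8%, slightly more because q(t) falls over time and the effect grows. The number dropped is 150 × 0.553 × 0.2 = 16.6.

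**Simulation (600,000 women per scenario, Kaplan-Meier).**

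| Event dates unusable | Dropped of 150 | 12 months | 18 months | Median (months) |
|---|---|---|---|---|
| 0% | 0 | 63.0% | 51.2% | 18.7 |
| 5% | 4 | 63.8% | 52.2% | 19.3 |
| 10% | 8 | 64.6% | 53.2% | 20.0 |
| 20% | 17 | 66.5% | 55.6% | 21.8 |
| 30% | 25 | 68.7% | 58.4% | 24.2 |

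The 18-month shifts are +1.0, +2.0, +4.4 and +7.2 points. In 2,000 sets of 150 women the mean 18-month shift was +2.1 points at 10% and +4.5 at 20%.

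**Overall survival.** With an assumed 2-year survival of 70%, the estimate becomes 72.0% at m = 10% and 74.2% at m = 20%.

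**Alternatives at m = 20%, 18 months.**
- Censoring the woman at her event instead of dropping her is worse: the hazard factor is 1 − m, so 0.512^0.8 = 58.5%.
- Keeping the event with its date known to within half a month restores 51.2%.
- Losing dates equally for events and non-events also gives 51.2%.

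**The case against.** **Partial dates.** A reader might infer that every woman without a full date is removed. The documents do not say so. Both rules speak of missing data, and neither calls a month-and-year date missing. The SAP reports time from diagnosis in months, and month-level times can be analysed without imputation. The rule plainly reaches only wholly unknown dates, probably a smaller group. This objection stands; what remains is that the status of month-only dates is not stated.

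**Certainty of the bias.** A reader might also infer that the curves are certainly inflated. That needs m > c. It is plausible, but the documents do not show that every event-free woman has a last-contact date. This stands as a condition.

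**Available-case reading.** The rule can be read as ordinary available-case analysis that never considered undated events. That may be the intent, but applied to Kaplan-Meier it has the same effect.

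**Redaction.** Text after Protocol 9.7 and in the SAP's clinical-outcome section is blacked out, and the visible SAP has no Kaplan-Meier method. Event and censoring conventions could sit there. A rule imputing dates would contradict SAP section 6; an interval-censoring rule would not. This also stands.

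**Size and safeguards.** The share of undated events is assumed throughout. The sampling error at 150 women is about √(0.512 × 0.488 / 150) = 4.1 points, so the 10% case is about half of one standard error. Physician queries and forced entry reduce the problem, but they cannot recover a date that the chart does not hold. The study tests no hypothesis, but a descriptive proportion can still be biased.

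**Conclusion.** The point holds in conditional form. Both documents state an unqualified rule; applied to a known but undated progression or death, it removes an event and keeps the non-events. The estimates are too high if, and to the extent that, dates are missing more often for events than for last contact. Under the stated assumptions the 18-month inflation is about 1 point at 5% unusable dates, 2 at 10% and 4 to 5 at 20%. The actual share is unknown, and redacted text may hold a relevant convention. This should be settled before database lock, because the correction is cheap and the loss would otherwise go unreported.

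**What to change.** Add a date-only exception to Protocol 9.7 and SAP section 6, and leave the ban on imputation in place for all other variables.

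- **Month known:** use the date, set to mid-month and bounded by palbociclib start and the adjacent known contacts.
- **Event known, no usable date:** keep the woman in the analysis as interval-censored between the last date known event-free and the first date known to have had the event, or show results at both limits. Use the midpoint only when that interval is short, and not when the upper limit is merely the data-collection date. In a simulation of that case with 20% undated, the midpoint gave 12-month progression-free survival of 67.3%, against 66.8% from dropping the women and 63.0% with complete dates.
- **Reporting:** give the number of partial and of unknown event dates, and the number of event-free women without a last-contact date. The last count shows whether the condition for upward bias is met.

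The cost is a few lines of protocol and SAP text, a little code and, if not already present, a month/year option on the eCRF date fields. The downside is a small added assumption about dates, which the two limits make visible.

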## 9.8 Quality Control

To improve data quality the following actions will be undertaken:

- Provision of standardized instructions on study design, methodology and procedures.
  - Physicians will be contacted via email or telephone and an overview of the study will be provided (detailing study objectives, patient inclusion criteria, correct completion of eCRF and interview and any other logistical aspects of the study).
  - Follow-up with the physicians to ensure queries are resolved quickly.
- The electronic materials will be tested thoroughly to ensure that all questions appear correctly on screen, allow easy interpretation/completion and that all routing and logic checks are working correctly. As such, there should be no missing data (given the online nature of the study, the physician will have to complete a question before he/she is able to move on the next) however, ‘don’t know or unknown’ will be valid responses.
- To improve and secure data quality, automatic data checks upon data entry will be done within the eCRF. In the eCRF, plausible ranges of values for numeric data entries as well as logical data entries and listings will be provided for each entry field. Based on this, checks on completeness and plausibility will be performed upon data entry in the eCRF. All corrections will be visible from the systems audit trail.
- No regular monitoring or source data verification is planned in this study. However, in case of decreasing compliance (ie, of missing data, data discrepancies, protocol violations, etc.) a for-cause audit or risk-based monitoring visit will be performed.

## 9.9 Limitations of the Research Methods

A key limitation of a study of this nature is the reliance on accurate, complete eCRFs; which is dependent on the correct completion of the study materials and the availability of a detailed, complete patient records. We have outlined several important quality control steps to be taken as part of the study procedures to minimize the impact of this. Notably, to reduce the administrative burden on all physicians, the materials will be as short and user-friendly as possible.

The representativeness of the sample is limited to the consulting population for participation, who has been previously prescribed palbociclib combination with aromatase inhibitor (as prescribed by the Physician) in menopausal state as initial endocrine therapy in MBC or with fulvestrant after progression on prior endocrine therapy. We will not collect data from patients from non-participating physicians, thus introducing a potential selection bias. To minimize the risk of bias, multiple physicians will be recruited from a diverse geographical spread and mixed private/public practice where possible. To eliminate any patient identification bias during data collection a systematic patient selection criterion will be included and stressed to each participating physician. This will be further defined in the

eCRFs, but will consider the date of palbociclib approval for each indication. Patients who received palbociclib prior to approval or any other indication other than mentioned in the protocol will not be represented in this study.

Due to the observational design of the study, treatments received by patients may be subject to a channeling bias and thus must be interpreted with caution.

## **9.10 Other Aspects**

Not applicable.

# **10. PROTECTION OF HUMAN SUBJECTS**

## **10.1 Patient Information**

All parties will comply with all applicable laws, including laws regarding the implementation of organizational and technical measures to ensure protection of patient personal data. Such measures will include omitting patient names or other directly identifiable data in any reports, publications, or other disclosures, except where required by applicable laws.

The personal data will be stored at the study site in encrypted electronic form and will be password protected to ensure that only authorized study staff have access. The study site will implement appropriate technical and organizational measures to ensure that the personal data can be recovered in the event of disaster. In the event of a potential personal data breach, the study site shall be responsible for determining whether a personal data breach has in fact occurred and, if so, providing breach notifications as required by law.

To protect the rights and freedoms of natural persons with regard to the processing of personal data, when study data are compiled for transfer to Pfizer and other authorized parties, patient names will be removed and will be replaced by a single, specific, numerical code, based on a numbering system defined by Pfizer. All other identifiable data transferred to Pfizer or other authorized parties will be identified by this single, patient-specific code. The investigator site will maintain a confidential list of patients who participated in the study, linking each patient's numerical code to his or her actual identity. In case of data transfer, Pfizer will maintain high standards of confidentiality and protection of patients' personal data consistent with the clinical study agreement and applicable privacy laws.

